1.1. Primary

- To assess early (all-cause) mortality rates within the first year of treatment in participants symptomatic with AIDS who started antiretroviral therapy with regimens based on Dolutegravir (DTG) or Efavirenz (EFV).

1.2. secondary

- Evaluate the proportion of participants with suppression of plasma viremia (CV less than 50 copies/ml), at different times of the study;
- Compare CD4+ gain over time for both groups;
- Compare the frequency of adverse events in participants using regimens with DTG and EFV.

2. Clinical Hypotheses

- DTG-based regimens are most effective in rapidly recovering CD4+ cells within the first year of therapy;
- DTG-based antiretroviral regimens are able to promote more rapid suppression of HIV plasma viremia than EFV;
- The group of participants treated with DTG-based regimens will have a lower rate of early mortality than those treated with the comparator drug.

3. Background and Justification

Currently available antiretroviral agents (ARVs) have made it possible to successfully treat virtually all HIV-infected participants, but some problems related to early mortality are still a matter of concern, especially in countries with limited resources (1,2). There are several reports showing that these participants have a significantly higher risk of death during the first few months of treatment compared to results observed in developed countries (3-11). One of the consistently detected risks for early mortality across these reports is low baseline CD4+ counts, although it does not appear to be the only reason for such an outcome. Other factors associated with higher mortality rates for participants starting antiretroviral therapy (ART) are anemia, low body weight, and ongoing opportunistic infections (12,13). Mortality rates for participants starting

antiretroviral therapy are quite variable, ranging from 1.8%, as demonstrated by a study carried out in Baltimore/USA, to values as high as 54%, in some areas of the African continent (3- 13).

A recent study comparing mortality rates between low-income and high-income countries in participants with AIDS starting ARV therapy demonstrated that the risk ratio for early death was 4.3 times higher (95% CI: 1.6 - 11 .8), in poorer countries, but dropped to 1.5 after seven months of therapy (6). Furthermore, another report comparing mortality rates among participants with AIDS in Brazil and the USA showed that individuals with CD4+ cell counts below 50 cells/mm³ had a 4.8 times greater risk of death after starting ART and the proportion of early deaths in the first three months was significantly higher for Brazilian participants compared to Americans (14).

In Brazil and other developing countries, there is still a large proportion of participants with AIDS who are diagnosed with AIDS, or who only seek health care for HIV infection in the final course of the illness. While a median first CD4+ cell count below 200 is a frequent finding for most countries in the world, it is expected to be even lower for participants living in resource-limited countries, making the problem of early mortality an issue. important concern.

Dolutegravir (DTG), an HIV-1 integrase inhibitor, is a potent and safe antiretroviral drug (14). Available evidence suggests that drugs in this class promote a more rapid reduction in HIV-1 plasma viremia, and a greater increase in CD4+ cell count, compared to EFV (15,16).

We propose to compare the impact of DTG versus EFV on early mortality rates in critically ill participants starting antiretroviral therapy (CD4+ <50 cells/mm³).

4. Study Design

This is a pilot, open-label study to prospectively assess the rate of early all-cause mortality in participants initiating ART with DTG-based regimens. Retrospectively, the medical records of participants who used EFV in the years 2014-2016 will be reviewed for comparison purposes.

5. Local

The study will be conducted by FBaI - Fundação Bahiana de Infectologia (Bahia) - Investigator: [name], and will include 4 additional sites in different Brazilian cities (Manaus, Natal, Florianópolis, and Porto Alegre)

6. Sample size

The total number of participants included in each study arm will be 92. The calculation of this sample size is detailed in the SAMPLE SIZE section.

6.1. Primary outcome

- The primary study endpoint will be the all-cause mortality rate in the first year of therapy for critically ill participants starting ART.

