10.1. Retrospective Group

Procedures	*Basal	Without 24	Without 48
TCLE	Not applicable		
Inclusion and Exclusion Criteria	X		
Medical History	X		
Adverse events	During the 48 weeks		
CV HIV-1	X	X	X
CD4+ / CD8 count	X	X	X
Biochemistry	X	X	X
Hematology	X	X	X

NOTE: A window of -30/+30 days for each visit will be acceptable for collecting this data.

*In the baseline visit, results of laboratory tests up to 90 days before screening will be accepted.

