10.2. Prospective Group

Procedures	Basal	Without 4	Without 8	Without 16	Without 24	Without 48
TCLE	X					
Inclusion and Exclusion Criteria	X					
Medical History	X					
Adverse events		X	X	X	X	X
CV HIV-1	X	X	X	X	X	X
CD4+ / CD8 count	X	X	X	X	X	X
Biochemistry	X	X	X	X	X	X
Hematology	X	X	X	X	X	X
Plasma Sample (Storage)	X					
Vitamin D3	X				X	X

NOTE: A window of -30/+30 days for each visit will be acceptable for collecting this data.

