10.8. Follow-up of Participants

All participants included in the protocol in the Prospective Group will be evaluated at baseline and after 4, 8, 16, 24, 36 and 48 weeks.

11. Study Duration

We estimate to recruit 92 participants over a period of 10 months. Considering the need for follow-up to 48 weeks, the total duration of the study will be 22 months. An additional two months will be spent on data analysis and manuscript preparation, giving us a total of 24 months to complete the study. The retrospective study should be

completed within the same time period. The selection of patients will be carried out considering eligible participants, consecutively, until the predicted N is reached.

12. Statistical Analysis and Justification of the Sample Size

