12.1. Sample Size Justification

Mortality rates are quite variable, depending on region, specific study, and population.

Most studies from African countries have shown that mortality in the first 3 months of ART for participants with CD4+ cells under the threshold of 50 cells/mm³ is generally greater than 30%, and may reach 52% in some reports.

On the other hand, in developed countries, most deaths in such a population usually occur after 7 months of therapy and the mortality rate is just as low (1.8% for the first year of treatment).

We estimated that early mortality for participants included in the EFV arm would be similar to the rates detected in African countries (around 30%). We hypothesize that participants using DTG-based regimens would benefit from faster recovery of CD4+ cell count and that they behave like those individuals starting antiretroviral therapy in developed countries (mortality rate around 2%).

Considering a lower limit of 2% (DTG arm) and an upper limit of 25% (EFV arm), a 95% CI and 80% power to detect differences between groups, it would be necessary to treat a total of 84 participants (42 on each arm). Adding 10% for dropouts, this would result in a total of 92 subjects (46 in each arm).

With the recent changes in treatment recommendations, all 92 participants will receive DTG. Participants who used EFV will be retrospectively evaluated, through the review of medical records, in an identical number (92 participants).

This will be an exploratory pilot study.

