**Table 1 - Variables analyzed to determine comparability**

Variable	Analysis method
Basal age	One-way ANOVA/KW
Basal VL	One-way ANOVA/KW
CD4 + basal	One-way ANOVA/KW

The primary efficacy endpoint is the number (%) of participants who achieved the primary endpoint (HIV-1 Viral Load RNA <50 copies / ml) at week 48 (or discontinuation) visit. Participants will be counted as non-responders if they do not attend Week 48 (or term).

The DTG treatment group will be compared to the EFV group with respect to the percentage of responders using a chi-square test. Two-tailed, 95% confidence intervals for the percentage of responders will be calculated for each treatment group.

The following table identifies the secondary endpoints of effectiveness and the methods used to analyze them.

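### Mortality is defined over the first year, but planned follow-up ends at week 48 with a 30-day window either side and no common cut-off day for deaths

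*Protocol*

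**What the plan says.** The one-year horizon appears in the primary objective (Protocol 1.1), in the primary outcome (6.1: "The primary study endpoint will be the all-cause mortality rate in the first year of therapy for critically ill participants starting ART") and again among the primary efficacy parameters (10.5).

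Follow-up is shorter. Under Protocol 10.8 the prospective participants "will be evaluated at baseline and after 4, 8, 16, 24, 36 and 48 weeks", and week 48 is the last evaluation. Section 11 says: "Considering the need for follow-up to 48 weeks, the total duration of the study will be 22 months". The note under the prospective schedule (10.2) reads: "A window of -30/+30 days for each visit will be acceptable for collecting this data".

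The retrospective schedule (10.1) also ends in a week-48 column, carries the same window note, and collects adverse events "During the 48 weeks".

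For the analysis, Table 2 in both Protocol 12.5 and the SAP lists the proportion of deaths with a chi-square test and gives no time point. The general considerations in both documents say that missing data are not estimated, except in the responder analysis.

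**The concern.** A crude proportion of deaths is a valid one-year risk only if every participant's status is known on the same day. Here the stated horizon is day 365, the planned end is day 336, and an in-window last visit may come as early as day 306. Someone seen alive at a week-48 visit on day 306 who dies on day 340 has died within the first year, but nothing in the plan arranges for that death to be found. Nor does the plan say whether such a person is a survivor, a missing value or a censored observation. Two analysts working from the same data could report different primary results.

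The late part of the year is not plainly negligible under the plan's own reasoning. Section 12.1 says that in developed countries "most deaths in such a population usually occur after 7 months of therapy", and it takes those countries as the model for the DTG group.

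**Working it through.** **1. The plan's own figures**
- Sample size (Protocol 12.1): 2% versus 25%, two-sided 5% level, 80% power. The usual two-proportion formula gives 34 per arm. With the continuity correction it gives 42, as stated. This point does not affect the sample size.
- Duration (section 11): 10 months of recruitment + 12 months = 22 months. Since 336 / 30.44 = 11.0 months, the protocol is treating 48 weeks loosely as a year.

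**2. Days not observed**
- Nominal last visit: 48 × 7 = day 336. Window: 336 − 30 = day 306 to 336 + 30 = day 366.

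| Last visit | Days of the year not covered | Share of 365 days |
|---|---|---|
| Day 306 (early edge) | 365 − 306 = 59 | 16.2% |
| Day 336 (nominal) | 365 − 336 = 29 | 7.9% |
| Day 366 (late edge) | 0 | 0% |

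**3. Expected deaths missed in the DTG group**
- Expected deaths: 0.02 × 92 = 1.84.
- Seven months is 7 × 365 / 12 = day 213, which leaves about 152 days to day 365.
- Assumption: a share *s* of deaths falls after seven months, spread evenly over those 152 days. The documents say only that most do, and only for developed countries, so *s* is taken from 50% to 100%.
- Share missed = *s* × (days not covered) / 152.

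| All last visits on | *s* = 50% | *s* = 100% |
|---|---|---|
| Day 306 | 19.4%, 0.36 deaths, observed rate 1.6% | 38.8%, 0.71 deaths, observed rate 1.2% |
| Day 336 | 9.5%, 0.18 deaths, observed rate 1.8% | 19.1%, 0.35 deaths, observed rate 1.6% |

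If deaths were instead spread evenly over the whole year, the figures would be 0.30 deaths (day 306) and 0.15 deaths (day 336). The day-306 row supposes that every participant is seen at the early edge, so it is an upper bound.

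**4. Direction of any bias**
- Expected EFV deaths at the planning rate: 0.25 × 92 = 23.
- With the same truncation in both groups, the numbers missed are in the ratio 1.84 × *s*(DTG) to 23 × *s*(EFV).
- On the difference in proportions these balance when *s*(EFV) = (1.84 / 23) × *s*(DTG) = 0.08 × *s*(DTG). On the ratio scale they balance when the two shares are equal.
- If no EFV deaths fall late, truncation flatters DTG. If 25% do and all visits are on day 306, 0.25 × 0.388 × 23 = 2.2 EFV deaths are missed, more than the 0.71 DTG deaths at most, and the difference shrinks.
- The direction therefore depends on the timing of deaths in each group, which the documents do not give for these participants.

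**The case against.** The strongest reply is that 48 weeks is simply the protocol's working year. Section 11 budgets it as 12 months, and the study is described as an exploratory pilot concerned with early deaths. The window note governs collection of visit data. It does not say that a death learned of later would be ignored, and serious adverse event reporting covers death without a stated end date. This stands as far as it goes: the gap is one of planning and definition, and the last weeks of the year are peripheral to the main question. It does not supply a cut-off day or a way of finding late deaths. The algorithm in 10.5 that treats absence, switch or discontinuation as failure does not close the gap either, because a participant who attended an early week-48 visit is not absent.

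Three stronger readings are tempting and are not supported.
- A reader might infer that EFV charts would show deaths through day 365 or later while DTG deaths stop at the last visit, so that the error favours DTG. Section 10.1 gives the EFV group the same last column, the same window and a 48-week event period. Differential ascertainment is possible, since no mortality cut-off is written, but it is not shown.
- A reader might take the SAP's phrase "at week 48 (or discontinuation) visit" to mean that follow-up for death ends when treatment stops. That phrase defines the viral-load responder endpoint and does not concern death.
- A reader might take 59 days as the typical loss. It is the worst case for one participant in a symmetric window.

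**Conclusion.** The point holds as a modest correction. As written, the schedule does not deliver the one-year mortality rate named as the primary outcome, and no common day is set to which deaths are counted. The shortfall is 29 days at the nominal visit and ranges from 0 to 59 days.

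At the protocol's planning rates, fewer than one DTG death would be missed (0.18 to 0.71 of 1.84), against about 23 expected EFV deaths, so the planned contrast would not be overturned. These figures rest on the 2% and 25% rates, on 50% to 100% of DTG deaths falling after seven months, and on an even spread thereafter. A higher DTG death rate would raise the number missed in proportion. A bias towards DTG is possible but not established.

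**What to change.** In Protocol 6.1, 10.1 and 10.2 and in the SAP, set one mortality cut-off day, counted from first dose, for both groups. Either option would do:
- **Day 336.** Define the endpoint as death by week 48, and confirm vital status to day 336 even when the visit took place early.
- **Day 365.** Keep the one-year endpoint, and ascertain vital status at day 365 in both groups by a call or record check.

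Under either option:
- apply the cut-off whatever the visit date and whether or not treatment was stopped;
- exclude deaths after it in both groups;
- do not count a participant last seen before it as a survivor without a later contact. For example, censor that participant at last contact in a Kaplan-Meier estimate read at the cut-off, and report the number so handled in each group.

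The cost is one call or record check per participant and a cut-off date for the chart review, or, under the first option, a slightly shorter stated horizon. The day-365 option needs no longer study, because 10 months of recruitment plus 12 months already fits the stated 22.

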6.2. Secondary Outcomes

- The proportion of patients who achieved a Viral Load (CV) below 50 copies/ml at weeks 4, 8, 12, 24 and 48;
- Gain of CD4+ cells after 24 and 48 weeks
- Frequency of adverse events in participants receiving DTG or EFV therapy.

7. Inclusion criteria

7.1. Retrospective Group

- Participants with confirmed HIV-1 infection (Western Blot positive or HIV-1 RNA $>>1,000$ copies/ml);
- Having used EFV as initial therapy in the years 2013-2016;
- Baseline CD4+ cell count equal to or less than 50 cells/mm³;
- Age equal to or greater than 18 years;
- Plasma viral load immediately prior to initiation of therapy ≥ 1000 HIV-1 RNA copies/ml.

7.2. Prospective Group

- Participants with confirmed HIV-1 infection (Western Blot positive or HIV-1 RNA ≥ 1000 copies/ml);
- Not having previously used any ARV (treatment-naïve participants);
- Baseline CD4+ cell count equal to or less than 50 cells/mm³;
- Age equal to or greater than 18 years;

- Plasma viral load \geq 1,000 HIV-1 RNA copies/ml in the last 30 days.
- The participant or his/her legal representative is willing and able to understand and provide signed and dated free and informed consent prior to any study procedure.

8. Exclusion Criteria

[figure not shown]
8.1. Retrospective Group

- Asymptomatic individuals (at the beginning of ART).

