8.2. Prospective Group

- Undetectable plasma viral load at screening;
- CD4+ cell count > 50 cells/mm 3 ;
- Age less than 18 years old;
- Asymptomatic individuals.

9. Study Flowchart

10. Study Procedures

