10.3. Basal Critical Ratings

The Informed Consent Form (TCLE) must be obtained from each potentially eligible individual (or their legal representative) by the study center staff before any study procedure. The TCLE must have been approved by the Research Ethics Committee (CEP). Upon signing up, participants will complete initial assessments to determine their eligibility. Each participant selected for evaluation of inclusion in the study will be assigned an allocation number, given sequentially in chronological order of inclusion.

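### The undefined exclusion of asymptomatic patients is judged before any outcome for DTG but from outcome-bearing charts for EFV, so the comparator can be selected in an outcome-dependent way, with size and direction unknown

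*Protocol*

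**What the plan says.** The primary objective (protocol 1.1) concerns "participants symptomatic with AIDS who started antiretroviral therapy". Section 8.1 puts this into effect for the EFV group by excluding "Asymptomatic individuals (at the beginning of ART)". Section 8.2 excludes "Asymptomatic individuals" from the DTG group and gives no time point. Neither the protocol nor the SAP defines the term, lists qualifying conditions, or says how to class a chart that does not mention symptoms.

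The other severity-related criteria are laboratory values. Both groups need "Baseline CD4+ cell count equal to or less than 50 cells/mm³" and a viral load of at least 1,000 copies/ml.

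The two groups are assessed differently:

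- **DTG (10.3):** "Upon signing up, participants will complete initial assessments to determine their eligibility".
- **EFV (section 4):** "Retrospectively, the medical records of participants who used EFV in the years 2014-2016 will be reviewed for comparison purposes". Section 7.1 gives the years as 2013-2016. Section 10.1 takes eligibility and medical history at baseline, and the 24- and 48-week data, from the same review. It allows 30 days either side of each visit.

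On the order of selection, section 11 says: "The selection of patients will be carried out considering eligible participants, consecutively, until the predicted N is reached". Table 1 (protocol 12.5 and SAP) compares age, viral load and CD4+ only. Table 2 compares the proportion of deaths by chi-square test.

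**The concern.** One word does different work in the two groups. For a DTG candidate the symptom judgement is made when nobody knows how the patient will fare. For an EFV patient the person judging can see whether the patient died, and the evidence depends on how fully someone wrote up the visit years ago. If the completeness of notes, or the reading of them, is related to survival, then membership of the EFV group depends on the primary outcome.

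One plausible route is that a patient who died early left detailed admission notes and is classed as symptomatic, while a similar patient who did well left a brief clinic note and is excluded. That would raise EFV mortality and favour DTG. Losses among early deaths would act the other way.

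The planned safeguards do not reach the problem. Consecutive selection applies to patients already judged eligible, so it comes after the symptom judgement. Section 3 names anemia, low body weight and ongoing opportunistic infection as mortality factors, but none of them is in Table 1. A difference in clinical severity could go unseen, and no adjusted analysis is planned.

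**Working it through.** **1. The plan's own figure.** The sample size (12.1) uses 2% against 25% mortality, two-sided 0.05 and 80% power.

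- Uncorrected: n = [1.96·√(2·0.135·0.865) + 0.8416·√(0.25·0.75 + 0.02·0.98)]² / 0.23² = 33.4, so 34 per arm.
- With continuity correction: (33.45/4)·[1 + √(1 + 4/(33.45·0.23))]² = 41.7, so 42 per arm, as stated.
- Dropout: 84 × 1.10 = 92.4, against the stated 92.

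This figure is not in dispute and does not depend on the symptom criterion.

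**2. Inputs for the bias check.**

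- From the documents: 92 patients per group (12.1), and a two-sided chi-square test at 0.05 (12.3, Table 2).
- Assumed, because the documents give no value: true mortality p = 15% in both groups; f, the share of eligible EFV survivors lost through the symptom judgement or incomplete records; and g, the same share for EFV deaths. The DTG group is taken as unaffected.

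**3. Formula.** Observed EFV mortality = p(1−g) / [p(1−g) + (1−p)(1−f)].

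Example with f = 30% and g = 10%: 0.15·0.90 / (0.15·0.90 + 0.85·0.70) = 0.135/0.730 = 18.5%.

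The rejection rate comes from exact enumeration of both binomial distributions, 92 against 92, with the uncorrected chi-square test. There is no true drug effect, so every rejection is false.

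| Survivors lost (f) | Deaths lost (g) | Observed EFV mortality | False rejections |
|---|---|---|---|
| 0% | 0% | 15.0% | 4.9% |
| 10% | 0% | 16.4% | 5.7% |
| 20% | 0% | 18.1% | 8.5% |
| 30% | 0% | 20.1% | 14.8% |
| 40% | 0% | 22.7% | 26.6% |
| 20% | 10% | 16.6% | 5.9% |
| 30% | 10% | 18.5% | 9.5% |
| 30% | 20% | 16.8% | 6.2% |
| 30% | 30% | 15.0% | 4.9% |
| 10% | 20% | 13.6% | 5.8% |

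**4. The same check at the protocol's EFV rate.** With p = 25% in both groups, f = 30% and g = 0 give 32.3% observed EFV mortality and 19.5% false rejections. With f = 0 and g = 20%, observed EFV mortality is 21.1%.

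**5. Could this produce the whole planned contrast?** With g = 0, the survivor loss needed to turn a true p into 25% is f = 1 − (p/0.25 − p)/(1 − p).

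- p = 2%: 1 − 0.06/0.98 = 94%
- p = 10%: 1 − 0.30/0.90 = 67%
- p = 20%: 1 − 0.60/0.80 = 25%

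**6. Reading.** The bias depends on the difference between f and g. It is zero when they are equal and reverses when deaths are lost more often.

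**The case against.** A reader might infer that EFV survivors with sparse notes are dropped, so that EFV mortality is inflated and DTG favoured. The documents do not support that. Section 8.1 excludes asymptomatic patients, not charts that are silent on symptoms, and nothing describes note completeness by outcome. The opposite is also possible. Section 7.1 requires a baseline CD4+ count and a viral load from immediately before therapy. Patients who die soon after starting may have short charts or lack these results, which would remove EFV deaths.

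Three further points can be made for the plan:

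- Section 8.1 ties the status to the beginning of ART, and 10.1 places eligibility and medical history at baseline. This stands, but it dates the condition and not the evidence. Read literally, the 30-day window in 10.1 lets later notes count towards the baseline record.
- Both groups share the CD4+ cut-off, and section 3 describes the patients as critically ill. The symptom rule may therefore remove few charts. This also stands, since the number is unknown.
- Section 12.1 calls the study an exploratory pilot, and hindsight is partly inherent in a retrospective comparator. That lowers the stakes. It does not remove the issue, because a two-sided test of the groups at 0.05 is still planned and the outcome-aware step is avoidable.

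**Conclusion.** The point holds as a weakness in how the comparator is selected, not as a demonstrated bias towards DTG. The only clinical-severity criterion is undefined. It is applied before the outcome in one group and with the outcome in the record in the other, and no planned comparison would reveal differential selection.

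The effect could be negligible or material. In the assumed scenarios at 15% true mortality, observed EFV mortality runs from 13.6% to 22.7% and false rejections from 4.9% to 26.6%. The large values need 30-40% loss of survivors with few or no deaths lost, and the documents give no evidence for that. The mechanism alone could not plausibly turn a true 2% into the planned 25%. All of this rests on assumed loss rates and on an unaffected DTG group.

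The change should be made because it is cheap and limits the bias in either direction.

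**What to change.** 1. In 8.1 and 8.2, replace the undefined word with one common list of qualifying conditions or symptoms. At least one must be recorded in a note dated on or before the first ART dose. State how a chart with no symptom entry is classed.
2. For EFV, screen charts consecutively. Complete and lock the eligibility list from pre-ART records before any follow-up or vital status is abstracted.
3. Log every excluded chart with its reason.
4. Add a sensitivity analysis of mortality that includes every otherwise eligible EFV chart in the screened series, whatever its symptom record. Present it as a sensitivity analysis and not as a conservative bound. Charts that lack a pre-ART CD4+ count or viral load would still be excluded, and deaths could be among them.

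The cost is an amendment to one criterion in each group, a two-step abstraction order that the same staff can follow, and a few more charts to abstract. The sensitivity analysis will dilute the EFV group with some truly asymptomatic patients. The lock has to come first, because outcome-blind selection is hard to restore once charts have been abstracted with outcomes in view.
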